The PainSMART-project is a research program with a collective suite of studies utilising mixed methods, centred on a randomised controlled, superiority trial with two parallel groups. A 1:1 group allocation ratio will be applied. The control group and statistician will be blinded. One independent statistician will be blinded for the primary analyses. Another independent statistician will be responsible for database development and linking of patient and physiotherapist data. The results of the RCT will be reported according to the Consolidated Standards of Reporting Trials (CONSORT) statement and the CONSORT patient-reported outcomes checklist (Calvert et al., 2013; Schulz et al., 2010). The final phase of the RCT will include qualitative data collection which will be reported in line with the Consolidated Criteria for Reporting of Qualitative research (COREQ; Tong et al., 2007).

Study setting

This study is a multi-centre RCT that will be conducted at five primary care physiotherapy departments within the Swedish regions of Östergötland (RÖ) and Jönköping (RJL). All four physiotherapy departments within RÖ and one physiotherapy department within RJL have agreed to participate. Collectively these centres employ around 130 physiotherapists and provide initial consultations to approximately 30 000 unique individuals in a one-year period. A list of the participating physiotherapy departments is available from the corresponding author on request.

Eligibility criteria

Potentially eligible patient participants are all adults (18 years or older) seeking primary care for MSKP who are triaged and booked for an initial physiotherapy consultation at one of the participating physiotherapy departments. Inclusion and exclusion criteria are shown in Table 1. A flow chart of the patient participants' path through the study is shown in Figure 1. All physiotherapists who provide care to patients booked for a consultation for MSKP at one of the participating physiotherapy departments are eligible to participate.

Table 1. Randomised controlled trial inclusion & exclusion criteria

Inclusion criteria

 Patients who, via telephone or online text-based triage, are judged to have benign MSKP and are booked for an initial physiotherapy consultation Adult patients (18 years or older)
Exclusion criteria

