The intervention group will be exposed to the film on two occasions. Access to the film is imbedded within the intervention group's online questionnaires and the film is first made available immediately following completion of baseline background and PROM data collection. Further exposure occurs at the data collection time point prior to the initial physiotherapy consultation. The time from baseline to the initial physiotherapy consultation will vary for each participating patient depending on clinical prioritisation and the accessibility of initial consultations at the participating physiotherapy departments. The film is hosted on RÖ's Quick channel, viewable on any electronic device and is exclusively available to the intervention group via the questionnaires. In order to reduce the risk of contamination bias the film is not shareable or available via online searching.

All participating physiotherapists will provide initial consultations to patients in both the intervention and control groups. For the intervention group the initial physiotherapy consultations will take place as usual with the addition of the discussion around the film and questionnaires. Any tailoring of the physiotherapists' responses to the patients' answers will occur according to the preferences and skills of each individual physiotherapist. The physiotherapists will not have access to the results of the questionnaires completed by the patients prior to the initial consultation.

Why

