
dimensions they cover are central to a high-quality consultation (Epstein et al., 2005; Lehman, 2017).

- *Evaluation of physiotherapists' perception of the degree to which the participating patients in the respective groups are prepared for their initial physiotherapy consultation*

All physiotherapists who have conducted at least one of the approximately 490 initial physiotherapy consultations in the RCT will anonymously rate, on a scale from zero to ten, to what extent they felt that the patients in the film respective control groups were prepared for their initial consultation (i.e. to what extent the patient seemed to have reflected over biopsychosocial factors that may have influenced their pain experience and its impact on function and wellbeing prior to the initial consultation). These follow up questions are aimed at evaluating the consulting physiotherapists' impression of the impact of the film and questionnaires on the participating patients' degree of biopsychosocial understanding of MSKP at their initial consultations.

- *Qualitative evaluation of the effects of the PainSMART-strategy on communication at the initial physiotherapy consultation*

The PainSMART-strategy is a complex intervention in which the potential mechanisms of effect are diverse (Lewin et al, 2009). The quantitative part of the RCT will provide limited insight into how the PainSMART-strategy directly influences patient-physiotherapist communication at the initial physiotherapy consultation. Therefore, to further analyse the effects of the PainSMART-strategy on the initial consultation the concluding phase of the RCT will include a qualitative data collection.

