Physiotherapist consent and background data will be collected via Webropol questionnaires prior to the start of patient recruitment. English language copies of the data collection questionnaires (patient and physiotherapist PROMs and PREMs) are available from the corresponding author on request. The physiotherapists' evaluations of the initial consultation will be sent to the study coordinators via the messenger function of the electronic journal system within RÖ and RJL. All physiotherapists who have conducted at least one initial PainSMART consultation in the RCT will be sent a follow up Webropol questionnaire containing four questions. These four questions ask the physiotherapists to self-report their adherence to the study protocol for each group and rate their experiences of the participating patients' degree of preparedness for the initial consultations. For physiotherapists who consent to continue participation in the RCT for the qualitative phase, additional data will be collected via Dictaphone audio recordings of the initial physiotherapy consultation. The audio recordings will then be uploaded to Linköping University's secure NextCloud service.

Sample size

The sample size calculation for this study is based on its primary hypotheses. The calculations are based on the MCID of $2 \pm SD/4$ for the NRS for pain intensity and a minimal detectable change of $11.52 \pm SD/23.20$ for the PSEQ-10 (Dube et al., 2021; Olsen et al., 2017; Olsen et al., 2018; Ostelo et al., 2008). Sample size calculations were computed for both primary outcomes (NRS and PSEQ-10) using a Cohen's f effect size of = 0.25 (i.e. small-moderate) and a one-sided p-value of $p=0.05$ plus a statistical strength of 0.8 (=Power 80%). The largest sample size calculated was for analysis of the NRS ($n = 102$ per group) and this was adopted as the sample size for this study. To enable mediation and sub-group analyses two subgroups are required. This gives a total sample size of 408 patients. A drop-out rate of approximately 30% was factored into the randomisation sequence giving a total sample of 600 patients.

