Physiotherapists' experiences of the initial physiotherapy consultation will be measured using three questions adapted from the National Patient Survey, Sweden. The questions evaluate if they felt that they received sufficient information from the patient to adequately make clinical judgements regarding the patient's MSKP, whether they and the patient could reach a consensus regarding the patients MSKP and whether they felt the patient actively took part in decision making regarding their care. The questions are answered on a NRS score range: 0-10, where a higher score reflects a more positive experience in relation to each question.

- Time Frame: collected 24-48 hours post the initial physiotherapy consultation.
- Calculation to derive outcome:
 - Descriptive statistics and between group differences in each question. The questions will be matched for concordance with the patients' PREM questions.

Other measures

-Physiotherapist reported experience of the initial physiotherapy consultation

Physiotherapists' experiences as to what extent they perceived that the patients were prepared for the initial physiotherapy consultation (i.e., whether the patient seem to have reflected over biopsychosocial factors that may have influenced their pain experience and its impact on their function and wellbeing) will be asked through one question for each group. The question is answered anonymously via NRS, score range: 0-10, where a higher score reflects a perception of the patient being more prepared.

- Time Frame: collected after all participating physiotherapists had their final study consultation.
- Calculation to derive outcome:
 - Descriptive statistics and between group differences in each question.

-Physiotherapists' adherence to study protocol

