The mediator models will be adjusted for the baseline score in the dependent variable (outcome), the mediator as well as the potential pre-treatment confounders (MacKinnon, 2012). The interaction term between the intervention allocation and the mediator will be analysed to examine its impact on the indirect effects (MacKinnon et al., 2020). The interaction term will be adjusted for in the outcome model if indicated. The principle of ITT will be followed using full information maximum likelihood in the mediation analyses, if other methods are not indicated.

The results will be reported according to A Guideline for Reporting Mediation Analyses (AGReMA) (Lee et al., 2021).

[figure not shown]

Figure 2. Directed Acyclic Graph (DAG) of the causal pathways for the effect of the PainSMART-strategy on the outcomes pain intensity and pain self-efficacy via the hypothesized mediators and the estimated averaged effects adjusted for confounding effects. The potential confounders are measured at baseline. The indirect effect (ab-product) is the average intervention effect through the mediator. *a*, *a*-path (the intervention-mediator effect); *b*, *b*-path (the mediator-outcome effect); *c*, *c*-path (the total effect of the intervention on the outcome, without accounting for potential mediator); *c'* (the direct effect of the intervention on the outcome, that works through all other mechanisms excluding the selected potential mediator). BIPQ, Brief Illness Perception Questionnaire; NRS, Numerical Rating Scale; PSEQ-10, Pain Self-Efficacy Questionnaire.

Secondary exploratory analysis

Intervention fidelity

Physiotherapists' experiences as to the extent that they perceived the patients as being prepared for the initial physiotherapy consultation will be presented descriptively with means and SDs. The between group difference will be analysed using an independent sample t-test and presented as mean and CI. Analyses will be conducted for the intervention group on group mean change between before and directly after exposure to the film in MSKP illness perceptions (BIPQ item and total score) and on the question regarding reassurance as to the benign nature of MSKP (NRS). Paired sample T-test will be used for analysing the within group change. The results will be presented as means and CI. The intervention group's scores regarding the clarity of the film's key messages will be presented descriptively with means and SD for each question.

Exploratory mediation analysis

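### Film-group and control-group preparedness scores come largely in pairs from the same physiotherapists, but the SAP compares them with an independent-samples t-test

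*SAP*

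**What the plan says.** The rater is the physiotherapist, not the patient. In the Protocol's PREM section, on perceived preparedness: "All physiotherapists who have conducted at least one of the approximately 490 initial physiotherapy consultations in the RCT will anonymously rate" on a 0-10 scale "to what extent they felt that the patients in the film respective control groups were prepared for their initial consultation". The SAP, under Other measures, says that the item "will be asked through one question for each group".

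Both scores are collected together. Under Physiotherapist data collection, the Protocol says that physiotherapists with at least one trial consultation "will be sent a follow up Webropol questionnaire containing four questions", which cover adherence and preparedness for each group.

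Physiotherapists are meant to work across both arms. Protocol, Where and how: "All participating physiotherapists will provide initial consultations to patients in both the intervention and control groups".

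The analysis is in the Intervention fidelity paragraph of the SAP. The scores are first summarised by mean and SD: "Physiotherapists' experiences as to the extent that they perceived the patients as being prepared for the initial physiotherapy consultation will be presented descriptively". The comparison of the two groups comes next: "The between group difference will be analysed using an independent sample t-test and presented as mean and CI". The same paragraph uses a paired t-test, but only for change from before to after the film in illness perceptions and reassurance. The matching Protocol section on analysis of PREMs mentions descriptive statistics and between-group differences without naming a test.

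**The concern.** An independent-samples t-test assumes that the film scores and control scores come from unrelated raters. Here one person who saw both arms supplies a score to each sample. A generous rater tends to score both groups high and a strict one to score both low. That shared component cancels in a within-rater difference, but the planned test leaves it in the error term.

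Nothing else in the SAP repairs this. The fallback under Statistical Principles concerns distributional assumptions, the Bonferroni rule there concerns repeated measures over time, and the physiotherapist covariates belong to the mediation models.

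What is at stake is the reading of one exploratory result. If the interval is wider than the data warrant, a real difference in perceived preparedness could be reported as no difference.

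**Working it through.** The plan gives no sample size, SD or power for this item, so there is no figure to reproduce.

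**Inputs from the documents.** One score per group per rater. The number of raters is limited by staffing: "Collectively these centres employ around 130 physiotherapists". There are 450 to 490 consultations. Allocation is simple 1:1 randomisation with no stratification by physiotherapist. Confidence intervals are two-sided 95%.

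**Assumptions (not in the documents).** Within-rater correlation r = 0.3/0.5/0.7, equal SDs in both groups (SD set to 1), 100 raters in all, true difference 0.3 SD. Errors and powers below are two-sided 5% normal approximations unless stated.

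**1. How many raters are paired?** Spread N consultations evenly at random over P physiotherapists and let q = exp(-N/(2P)). The share of raters with patients in both arms is then about (1-q)/(1+q).
- N = 450, P = 130: q = 0.177, share 70%.
- N = 490, P = 130: q = 0.152, share 74%.
- N = 450, P = 60: q = 0.0235, share 95%.
- N = 490, P = 60: q = 0.0169, share 97%.

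If caseloads are uneven, the share falls: simulation with 450 consultations gave 63% for 130 physiotherapists and 79% for 60. The data are therefore largely, but not fully, paired.

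**2. Upper bound: 100 complete pairs.** The planned SE is sqrt(2/100) = 0.1414. The true SE is sqrt(2(1-r)/100) = 0.1183/0.1000/0.0775.
- Width ratio 1/sqrt(1-r) = 1.20/1.41/1.83.
- Actual type I error 2(1-Φ(1.96/sqrt(1-r))) = 1.9/0.56/0.03%. For a one-sided 5% test it is 2.5/1.0/0.13%.
- Power of the planned test, 1-Φ((1.96×0.1414-0.3)/true SE) = 58/59/62%.
- Power of the paired test, Φ(0.3/true SE-1.96) = 72/85/97%.

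**3. Partial pairing: 70 pairs plus 15 one-arm raters per arm (85 scores per arm).** The planned SE is sqrt(2/85) = 0.1534.
- True SE of the same difference in means: 0.1534×sqrt(1-r×70/85) = 0.1331/0.1176/0.0998.
- Type I error of the planned test, 2(1-Φ(1.96×0.1534/true SE)) = 2.4/1.1/0.3%.
- Pairs-only SE, sqrt(2(1-r)/70) = 0.1414/0.1195/0.0926. The SE ratio of planned to pairs-only is 1.08/1.28/1.66. With t multipliers (168 and 69 df), the interval ratio is 1.07/1.27/1.64.
- Power of the planned test: about 50% at each r. Power of the pairs-only test: 56/71/90%.
- SE when all raters are used with their correlation modelled (r treated as known), sqrt(2/(70/(1-r)+15)) = 0.1319/0.1136/0.0897. Power is 62/75/92%.

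Simulated t-tests agree closely. Type I error for the planned test came out between 2.1 and 2.7% at r = 0.3, and power was up to about 3 points below these approximations.

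**4. Outside the expected range.** At r = 0 the planned test is correct, and dropping one-arm raters costs power: about 42% for pairs only against 50%. At r = -0.2 with complete pairs, type I error is 2(1-Φ(1.96/sqrt(1.2))) = 7.4%.

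**The case against.** The strongest reply has four parts.

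- **Not every rater is a pair.** One consultation is enough to be sent the form, and with under four consultations per physiotherapist at 130 staff (450/130 = 3.5; 490/130 = 3.8), simple randomisation will leave some who saw only one arm. This stands. A reader might infer from the Protocol's statement about both groups that the two samples are the same people throughout, but it does not guarantee that each physiotherapist meets both arms. The complete-pairs figures are therefore upper bounds. Partial pairing reduces the error without removing it.

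- **The error is on the safe side.** This also stands for any positive r. A reader might infer that a wrong test means more false positives. That needs a negative correlation, for which the documents give no support.

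- **The item carries little weight.** It is listed under Other measures, analysed as exploratory, and given retrospectively by raters who know the allocation. This stands. A reader might infer that the trial's main conclusions are affected. They are not: no primary outcome, confirmatory mediation model or per-protocol definition uses this score.

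- **Anonymity prevents pairing.** This does not stand. Both answers are on one questionnaire, so a record can be kept together without identifying the physiotherapist.

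**Conclusion.** The test does not match the data structure. Physiotherapists who saw both arms supply paired scores, and the planned standard error is right only if the within-rater correlation is zero.

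The likely effect is lost precision, and its size depends on quantities that the documents do not give. At r = 0.3 with partial pairing the planned interval is only about 7 to 8% wider than a pairs-only interval. At r = 0.7 it is about 64% wider. It would therefore be too strong to say that the interval is far too wide in every case.

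The mismatch itself is certain from the text. The figures rest on the assumed correlation, 100 raters, a 0.3 SD difference and the assumed 70/15/15 split. Given the exploratory scope and the conservative direction, the correction is low priority.

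**What to change.** In the SAP's Intervention fidelity paragraph, replace the independent-samples t-test for preparedness with a linear mixed model that has group as fixed effect and physiotherapist (identified by questionnaire record) as random intercept. Report the mean difference with its 95% CI. This respects the pairing and keeps one-arm raters, whom a pairs-only test would discard.

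Add a paired t-test among physiotherapists who rated both groups as a check. It also covers the case of a negative correlation, which a random intercept cannot represent. Report how many physiotherapists rated one group only.

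Keep both answers on one row in the anonymous export. The cost is a few lines of SAP wording and no new data.

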- Calculation to derive outcome:

- Number and proportion of analgesic consumption and type of analgesics in each group at the data collection time points as well as within and between group differences.

-Sick leave

Self-reported current sick leave for the presenting MSKP complaint is established via one question. Answer alternatives: Yes or No.

- Time Frame: collected at baseline, 24 -72 hours prior to the initial physiotherapy consultation, 24 hours post initial physiotherapy consultation and at three months post-baseline.
- Calculation to derive outcome:
 - Number and proportion of patients currently on sick leave at the data collection time points as well as within and between group differences.

-Healthcare visits

Self-reported visits for the presenting MSKP complaint to healthcare practitioners other than the physiotherapist involved in the trial. Answer alternatives: Yes or No.

- Time Frame: collected at baseline, 24 -72 hours prior to the initial physiotherapy consultation, 24 hours post initial physiotherapy consultation and at three months post-baseline.
- Calculation to derive outcome:
 - Number and proportion of visits to other healthcare providers from 24 -72 hours prior to the initial physiotherapy consultation and all prospective data collection timepoints thereafter, as well as within and between group differences.

Healthcare register data outcomes

-Healthcare visits and referrals

Data will be collected from the regional healthcare databases on:

1. Number of healthcare visits for MSKP
2. Number of referrals for diagnostic imaging
3. Number of referrals to tertiary care

- Time Frame: collected for each participating patient for the time period baseline to three months following completion of data collection for all participants.
- Calculation to derive outcome:
 - Number and proportion of referrals and health care visits from baseline to three month follow-up, as well as between group differences.

-Direct cost per patient

Direct cost per patient will be collected from the Östergötland and Jönköping healthcare regions databases (Rebus).

- Time Frame: collected for each participating patient during the study period after the completion of data collection for all participants.
- Calculation to derive outcome:
 - Health care costs (sek) per patient for the MSKP during the study period will be presented as a group mean and standard deviation. Between group mean difference will be analysed.

-Sick leave days

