Data on sick leave days will be collected from the Swedish social security database (Försäkringskassan).

- Time Frame: collected for each participating patient for the time period baseline to three months following completion of data collection for all participants.
- Calculation to derive outcome:
 - Number and proportion of sick leave days from baseline to three months follow-up, as well as between group differences.

Physiotherapist and patient reported experience measure outcomes (PREM)

-Patient reported experiences of the film

The perceived clarity of key messages in the film will be measured via rating the clarity for each message (eight) on a 0-10 NRS by patients in the intervention group. A higher score indicates a clearer message.

- Time Frame: collected directly post first exposure to the film in the intervention group.
- Calculation to derive outcome:
 - Descriptive statistics.

-Patient reported experience of the initial physiotherapy consultation

Patients' experiences of the initial physiotherapy consultation will be measured using seven questions adapted from the National Patient Survey, Sweden. The questions evaluate if the patients felt that they had the possibility to talk sufficiently about their MSKP, whether they felt included in decision making around their care, whether they had the opportunity to discuss any worries and concerns they had regarding their MSKP and to what extent they discussed what they could do themselves to improve their MSKP and health. The patients are also asked if they felt the physiotherapist considered their personal MSKP experiences and explained MSKP in a way that they could understand. The questions are answered on a NRS score range: 0-10, where a higher score reflects a more positive experience in relation to each question.

- Time Frame: collected 24 hours post the initial physiotherapy consultation.
- Calculation to derive outcome:
 - Descriptive statistics and between group differences in each question. Three of the questions will be matched for concordance with the physiotherapists' reported experienced questions.

-Physiotherapist reported experience of the initial physiotherapy consultation

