To ensure a temporal sequence between the treatment, mediator, and outcome, data was collected over four sequential time points: 1) baseline, prior to randomisation (primary outcome, mediators, confounders); 2) prior to the initial physiotherapy consultation (mediators); 3) 24 hour post initial consultation (mediators); and 4) three months post baseline (primary outcome).

Mediation models and causal model assumptions

Each of the hypothesised mediator's potential effect on each primary outcome will be tested in single mediator models. The potential mediating effect of change in the hypothesized mediators at time point 2 (after exposure to the film) and at time point 3 (after exposure to the whole PainSMART-strategy) will be analysed. An overview of the confirmatory mediator models is presented in Table 1. We assume there to be no confounding of the intervention–mediator and intervention–outcome relationships due to random allocation of the intervention (intervention or control group) (Valeri & VanderWeele, 2013). We assume there to be no confounding of the mediator-outcome relationship following adjustment for the sufficient set of potential observed confounders.

Table 1. Overview of confirmatory mediator models

Model	Mediator Pre physiotherapy consultation	Mediator Post physiotherapy consultation	Outcome 3 months post baseline
1	Illness perceptions	-	Pain intensity
2	Reassurance of benign nature of MSKP	-	Pain intensity
3	-	Illness perceptions	Pain intensity
4	-	Reassurance of benign nature of MSKP	Pain intensity
5	Illness perceptions	-	Pain self-efficacy
6	Reassurance of benign nature of MSKP	-	Pain self-efficacy
7	-	Illness perceptions	Pain self-efficacy
8	-	Reassurance of benign nature of MSKP	Pain self-efficacy

Confounding

Identified potential confounders of the mediator–outcome relationship will be adjusted for in the single mediation analyses. Potential confounders were identified using the disjunctive cause criterion, which involves selection of measured pre-intervention covariates that are hypothesised to be a cause of the mediator, outcome, or both (VanderWeele, 2019). The

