The secondary objective is to explore if pain self-efficacy mediates the effect of the PainSMART-strategy on health outcomes of interest. Based on an integration of the CSM and concept of self-efficacy, the effect of MSKP illness perceptions and level of reassurance of the benign nature of MSKP on pain self-efficacy act as a first step in the causal pathway of the PainSMART-strategy's effect on health outcomes. As a second step in the causal pathway in the integrated model, the effect in pain self-efficacy is hypothesized to mediate the effects

on health outcomes. The theoretical rationale underlying the hypothesised mediators in the PainSMART-strategy are explained in full in the trial protocol.

Outcomes and data collection

Outcomes (dependent variables) are health outcomes hypothesised to be improved by the PainSMART-strategy (pain intensity, levels of physical activity, Global rating of change, number of healthcare visits, analgesic medication use, sick leave days). The hypothesised mediator is pain self-efficacy measured with the PSEQ-10. Data collection of the outcomes and mediator is the same as for the primary mediation analyses, see “Mediation analyses”.

Models and causal model assumptions

The potential mediating effects of change in pain self-efficacy at time point 2 (after exposure to the film) and at time point 3 (after exposure to the whole PainSMART-strategy) on the outcome will be analysed. The causal model assumptions are the same as for the primary mediation analyses, see “Mediation analyses”.

Statistical analysis

Causal mediation analysis will be used to analyse the PainSMART’s indirect effects on health outcomes through improvement in pain self-efficacy (PSEQ-10). The mediation models will be estimated using path-analyses within the framework of Structural Equation Modelling.

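### In the exploratory mediation, sick leave days and register healthcare visits are totalled from baseline, so the outcome window overlaps the self-efficacy mediator and the claimed temporal sequence does not hold for these two outcomes

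*SAP*

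**What the plan says.** The SAP, under Exploratory mediation analysis, lists as dependent variables "pain intensity, levels of physical activity, Global rating of change, number of healthcare visits, analgesic medication use, sick leave days". The mediator is the PSEQ-10: "The potential mediating effects of change in pain self-efficacy at time point 2 (after exposure to the film) and at time point 3" are to be analysed, the latter following the whole strategy. On timing the section says only that "Data collection of the outcomes and mediator is the same as for the primary mediation analyses".

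The section it points to (Mediation analysis, Data collection) states: "To ensure a temporal sequence between the treatment, mediator, and outcome, data was collected over four sequential time points". There the mediators are taken at time points 2 and 3 and the outcome at three months.

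Under Outcome definitions, the register outcomes are counts over a period. For visits the derivation is "Number and proportion of referrals and health care visits from baseline to three month follow-up, as well as between group differences"; for sick leave it is "Number and proportion of sick leave days from baseline to three months follow-up". The Protocol (Healthcare register data) gives the same period. The SAP also has a self-reported visits item, answered yes or no at each questionnaire and excluding the trial physiotherapist.

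The mediation adjustment set (SAP, Confounding) includes days to the initial physiotherapy consultation and previous healthcare interventions, plus baseline mediator and outcome.

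**The concern.** The order treatment, then mediator, then outcome works when the outcome is a three-month rating such as the pain NRS. It does not carry over to a quantity that starts accumulating at baseline. Time point 2 is 24 to 72 hours before the initial consultation and time point 3 is 24 hours after it, so both normally fall inside the counting window. Sick leave days or visits during the wait are then part of the outcome although they came before the mediator.

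This matters because such events could themselves lower self-efficacy. A patient off work while waiting may report a lower PSEQ-10 as a result. The mediator-outcome path would then partly run from outcome to mediator. If the film also shifts PSEQ-10, the product of the two paths can differ from zero with no mediation at all. The answer at stake is exploratory question 4, whether self-efficacy mediates the effect on health outcomes.

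**Working it through.** The plan gives no figure for this overlap, so there is none to reproduce. The check has three steps.

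**1. Windows side by side**

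- Outcome window for register sick leave days and register visits: baseline to three months (SAP, Outcome definitions; Protocol, Healthcare register data). Taken here as 91 days.
- Mediator: time point 2 or time point 3 (SAP, Time frame for data collection).
- Wait *w* from baseline to consultation: varies by patient, with no mean or range stated (Protocol, Where and how). Same-day and next-day bookings are excluded (Protocol, Table 1), so some time before time point 3 exists for every eligible patient.
- No sentence in the SAP's mediation sections restricts the counts to the period after the mediator.

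**2. Share of the window before the mediator**

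Time point 2: (w−3)/91 to (w−1)/91. Time point 3: (w+1)/91.

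| Assumed wait (days) | Before time point 2 | Before time point 3 |
|---|---|---|
| 7 | 4/91 to 6/91 = 4% to 7% | 8/91 = 9% |
| 14 | 11/91 to 13/91 = 12% to 14% | 15/91 = 16% |
| 30 | 27/91 to 29/91 = 30% to 32% | 31/91 = 34% |
| 45 | 42/91 to 44/91 = 46% to 48% | 46/91 = 51% |

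These are shares of calendar time. They are not the size of any bias.

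**3. Can the overlap create a false mediator path?**

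An illustrative simulation used 408 patients, a mean of 3 events in 91 days, a 3-point film effect on PSEQ-10, and no effect of PSEQ-10 on later events. Each event during the wait lowered PSEQ-10 by an assumed 0, 2 or 4 points. Paths were fitted by least squares, with 500 runs per setting. All these inputs are assumptions. The table gives the share of runs in which the mediator-outcome path was significant at two-sided 0.05.

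| Points lost per early event | Count used | Wait 7 | Wait 14 | Wait 28 |
|---|---|---|---|---|
| 0 | Baseline total | 6% | 7% | 4% |
| 0 | After mediator | 7% | 7% | 4% |
| 2 | Baseline total | 10% | 26% | 75% |
| 2 | After mediator | 4% | 5% | 5% |
| 4 | Baseline total | 27% | 75% | 100% |
| 4 | After mediator | 7% | 5% | 4% |

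With 2 points lost, the mean indirect effect on the baseline total was −0.023, −0.042 and −0.081 events at the three waits. With the post-mediator count it was within 0.001 of zero.

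These runs gave every patient the same event rate. When rates vary between patients, early events also predict later ones. The post-mediator count alone then rejected in 6% to 33% of runs across the settings tried, and returned to about 5% once the early count was added as a covariate. Moving the start of the count is therefore not enough by itself.

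**The case against.** Several points on the other side are sound.

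- **Source of visits.** The SAP also defines self-reported visits, taken at separate questionnaires, and the exploratory section does not say which source it means. The word number fits the register count better than a yes/no item, but for visits the overlap is conditional on that reading. For sick leave days it is not, because a count of days exists only in the register data.
- **Reversal.** A reader might infer that the sequence is reversed. The documents do not support that for the totals: at waits of 7 to 14 days, 91% to 84% of the window still follows time point 3. Only the events before the mediator are in the wrong order.
- **The initial consultation.** It always precedes time point 3, so a reader might see it as a bias of its own. If the register counts it, it adds one visit to every attender, and a constant does not change a linear path among attenders. The self-reported item excludes the trial physiotherapist.
- **Length of wait.** The Protocol reports an interim analysis on 29 February 2024, after the first six weeks of recruitment, with about 229 patients having reported time points 2 and 3. Those patients reached time point 3 within about six weeks, so the 45-day row does not describe them. They are the early completers, so longer waits in others are not excluded.
- **Existing adjustment.** Days to consultation, previous healthcare interventions, employment and the baseline scores may reduce confounding. None of them records what happened between baseline and the mediator. The SAP's plan to analyse register outcomes as change to each time point also starts at baseline.

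None of this removes the overlap for sick leave days.

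**Conclusion.** The point stands as an overlap. For sick leave days, and for healthcare visits if the register count is meant, part of the outcome accrues before PSEQ-10 is measured, and the stated sequence fails. The share of time before time point 3 runs from about 9% to 51% for waits of 7 to 45 days, on an assumed 91-day window and assumed waits. The resulting bias cannot be sized from the documents. It depends on event rates and on whether early events affect self-efficacy, and with no such effect the simulation showed no inflation.

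The reach is limited to two of the six outcomes in an analysis labelled exploratory. A reader might extend the concern to the mediation analysis as a whole. The documents do not support that: all eight confirmatory models use pain intensity or PSEQ-10 at three months, and neither they nor the primary analysis is touched.

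**What to change.** In the SAP's exploratory mediation section, for these two outcomes only:

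1. State that number of healthcare visits means the register count.
2. Count visits and sick leave days from the day after the mediator questionnaire (time point 2 or time point 3, according to the model) to three months.
3. Allow for the length of the remaining window, with log days as an offset if a count model is used.
4. Include the count from baseline to the mediator questionnaire as a covariate in the outcome model. It is measured after randomisation and may itself be affected by the film, so causal wording should stay cautious.
5. Keep the baseline-to-three-months totals for the between-group comparison.

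The cost is a few sentences and a date filter. The register extract must carry event dates, including start and end of sick leave so that spells can be split. A scheduled date is needed where the mediator questionnaire was not returned, since the SAP keeps such patients through full information maximum likelihood. The downside is fewer events in an exploratory model. Register data are collected after questionnaire follow-up is complete for all participants, so the rule can be fixed before those data are seen.
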